#### **7.6.10.4   *Methemoglobin***

The number of subjects with highest methemoglobin post baseline >10% will be summarized.

A by-subject listing of these subjects will be provided.

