 - i) Participants who experienced prior Grade 1 to 2 checkpoint therapy-related immune-mediated AEs must have confirmed recovery from these events at the time of study entry, other than endocrinopathies treated with supplementation, as documented by resolution of all related clinical symptoms, abnormal findings on PE, and/or associated laboratory abnormalities. Where applicable, these participants must also have completed steroid tapers for treatment of these AEs by a minimum of 14 days prior to commencing treatment with study drug.
 - ii) Eligibility of participants with prior \geq Grade 3 checkpoint therapy-related immune AEs, will be considered on a case-by-case basis after discussion with the medical monitor (eg, asymptomatic isolated Grade 3 lipase elevations without clinical or radiological features of pancreatitis will be permitted to enroll).
- g) Prior palliative radiotherapy must have been completed at least 2 weeks prior to first dose of study drug. Participants with symptomatic tumor lesions at baseline that may require palliative radiotherapy within 4 weeks of first dose of study drug are strongly encouraged to receive palliative radiotherapy prior to enrollment.
- h) Participants must have blood methemoglobin levels within the ULN.
- i) Participants must have adequate marrow function for participants with solid tumor histologies as defined by the following:
 - White blood cells (WBC) $\geq 2000/\mu\text{L}$ (stable off any growth factor within 4 weeks of first study drug administration)

- Neutrophils $\geq 1500/\mu\text{L}$ (stable off any growth factor within 4 weeks of first study drug administration)
- Platelets $\geq 100 \times 10^3/\mu\text{L}$ (transfusion to achieve this level is not permitted within 2 weeks of first study drug administration)
- Hemoglobin $\geq 8.5 \text{ g/dL}$ (transfusion to achieve this level is not permitted within 2 weeks of first study drug administration)
- j) Participants must have adequate other organ function as defined by the following:
 - i) ALT and AST $\leq 3 \times$ institutional ULN
 - ii) Total bilirubin $\leq 1.5 \times$ institutional ULN (except participants with Gilbert's Syndrome who must have normal direct bilirubin)
 - iii) Normal thyroid function, subclinical hypothyroidism (thyroid-stimulating hormone [TSH] $< 10 \text{ mIU/mL}$) or have controlled hypothyroidism on appropriate thyroid supplementation

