7.4.3 Criteria to Resume Treatment of BMS-986205 and Nivolumab

Participants may resume treatment with study treatments when the drug-related AE(s) resolve to Grade ≤ 1 or baseline value, with the following exceptions:

- Participants may resume treatment in the presence of Grade 2 fatigue.
- Participants who have not experienced a Grade 3 drug-related skin AE may resume treatment in the presence of Grade 2 skin toxicity.
- For participants with Grade 2 AST, ALT, and/or total bilirubin abnormalities, dosing may resume when laboratory values return to baseline and management with corticosteroids, if needed, is complete.

- Participants with combined AST/ALT AND total bilirubin values meeting discontinuation parameters (Section 7.4.4) should have treatment permanently discontinued.
- Drug-related pulmonary toxicity, diarrhea, or colitis must have resolved to baseline before treatment is resumed. Participants with persistent Grade 1 pneumonitis after completion of a steroid taper over at least 1 month may be eligible for retreatment if discussed with and approved by BMS medical monitor/designee.

Participants with drug-related endocrinopathies adequately controlled with only physiologic hormone replacement may resume treatment after consultation with the BMS medical monitor/designee. Adrenal insufficiency requires discontinuation regardless of control with hormone replacement.

For participants who have BMS-986205 held for elevations of methemoglobin, dosing may resume when the methemoglobin levels have decreased to below the institutional ULN and any associated AEs have resolved to Grade \leq 1 or baseline value. Dose modification of BMS-986205 should be considered when resuming after a delay (see [Section 7.4.1](#)).

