10.3.2 Safety Analyses

All safety analyses for treated participants will be performed on the Safety Sample.

Endpoint	Statistical Analysis Methods
The occurrence of non-serious AEs, SAEs, AEs leading to discontinuation or death	All AEs will be listed and summarized by system organ class and preferred term for all treated participants and coded according to the most current version of Medical Dictionary for Regulatory Activities (MedDRA). Listing will be presented for deaths.
Clinical laboratory tests, vital sign measurements, ECGs, and physical examinations; and marked abnormalities in clinical laboratory test results	Vital signs, ECGs, and laboratory test results will be listed and summarized by time point. Any significant physical examination findings and marked abnormal clinical laboratory test results will be listed. ECG recordings will be evaluated by the investigator and abnormalities, if present, will be listed.
[REDACTED]	

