### **7.6.10    *Laboratory Parameters***

The analysis population for each laboratory test is restricted to treated subjects who underwent that laboratory test. Laboratory tests (in addition to the tests specified below) with CTC criteria collected in the specific studies may also be included in the summaries.

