#### **7.6.10.1   *Hematology***

The following will be summarized as worst CTC grade on-treatment per subject and as shift table of worst on-treatment CTC grade compared to baseline CTC grade per subject: hemoglobin (HB), platelets, white blood counts (WBC), absolute neutrophils count (ANC) and lymphocyte count (LYMPH).

A by-subject listing of these laboratory parameters will be provided.

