### **7.6.12 Electrocardiograms**

All of the available ECG parameter values from each subject will be included in the ECG data set.

Baseline values are defined as the last recorded values prior to the first dosing. For ECG parameters such as heart rate (HR), QT, QRS, QTcB, QTcF and PR, summary measures (n, mean, standard deviation, median, minimum, and maximum) will be provided.

A by-subject listing of all ECG measures and a listing of abnormal ECG interpretations will be provided.

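### SAP 7.6.10.4 reports methemoglobin only above 10%, so a consistent rise from the ULN up to 10% would appear in no methemoglobin output the SAP specifies

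*SAP*

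**What the plan says.** SAP 7.6.10.4 has two sentences. The first is "The number of subjects with highest methemoglobin post baseline >10% will be summarized". The second is "A by-subject listing of these subjects will be provided", so the listing covers only the participants just counted.

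No other SAP section that we can read plans a methemoglobin analysis:

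- SAP 7.6.10.1 names five hematology analytes (hemoglobin, platelets, white cells, neutrophils, lymphocytes). Methemoglobin is not one of them, although Protocol Table 9.4.1-1 places it under Hematology.
- SAP 7.6.10 adds an optional clause that names no test: "Laboratory tests (in addition to the tests specified below) with CTC criteria collected in the specific studies may also be included in the summaries".
- Reticulocytes, haptoglobin and LDH are not named in SAP 7.6.10.1 to 7.6.10.3.

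The protocol promises more: "Vital signs, ECGs, and laboratory test results will be listed and summarized by time point" (Protocol 10.3.2). It also gives the ULN a working role. At entry, "Participants must have blood methemoglobin levels within the ULN" (Protocol 6.1). After BMS-986205 has been held for methemoglobin, "dosing may resume when the methemoglobin levels have decreased to below the institutional ULN" (Protocol 7.4.3), together with recovery of any associated adverse events.

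**The concern.** Methemoglobin is sampled before dosing on Cycle 0 Days 1, 8 and 14, weekly in Cycle 1 and on Day 1 of each later cycle (Protocol Tables 2-2 and 2-3). That is a repeated continuous measure on a toxicity that has its own detection and treatment sections (Protocol 7.4.6 and 7.4.7). With about 12 participants, a common shift from baseline is likely to be the most informative thing these data can show. One yes/no cut at 10% cannot show it.

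Laboratory abnormalities belong to the primary endpoint. Protocol 7.4 also has the sponsor compare the risk profile with that of non-Chinese patients before considering a lower BMS-986205 dose or further enrolment. A study report that follows the SAP as written would carry no methemoglobin table or listing for anyone who rose above the ULN but stayed at or below 10%.

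**Working it through.** **1. The plan's own figure.** The documents give no numerical expectation for methemoglobin. The nearest figure is in SAP 5: with 12 participants, a 90% chance of seeing at least one case of an event with 18% incidence. Check: 1 − 0.82^12 = 0.908, which agrees. That figure concerns yes/no events. It says nothing about detecting a shift in a laboratory value.

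**2. Thresholds side by side.**

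| Level | Use in the protocol | Output in SAP 7.6.10.4 |
|---|---|---|
| ULN | Entry (6.1); reflex reticulocytes, haptoglobin and LDH (Tables 2-2 to 2-4); whether to sample in follow-up (Table 2-4); resuming BMS-986205 (7.4.3) | None |
| About 10%, with an associated Grade 3 AE | Reduction (7.4.1) and delay (7.4.2) of BMS-986205 | Count and listing above 10%, with or without an AE |
| 15% or more | Bar to Cycle 1 if drug-related (5.1); reduction (7.4.1); delay (7.4.2) | Inside the >10% group, not counted separately |

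Three participants peaking at 11% and three peaking at 16% therefore give the same count, 3/12.

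**3. Illustration of the gap.** All inputs are assumptions: baseline 1% for everyone, ULN anywhere from 1% to 3%, and twelve peaks of 3.2, 3.5, 4, 4.5, 5, 5.5, 6, 6.5, 7, 7.5, 8 and 9%.

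- Mean peak = 69.7/12 = 5.81%; median 5.75%.
- SAP output: 0/12 above 10%, and an empty listing.
- Above ULN: 12/12 for any ULN from 1% to 3%, since the smallest peak is 3.2%.
- Mean change = 5.81 − 1 = 4.81 points. The SD is 1.85, so the 95% CI is 4.81 ± 2.201 × 1.85/√12, or 3.6 to 6.0.
- At 15% or more: 0/12.

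**4. How far this depends on the assumed spread.** If peaks are normal with mean μ and SD σ, P(0/12 above 10%) = Φ((10 − μ)/σ)^12.

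| μ, σ (%) | P(0/12) | Expected number above a 3% ULN |
|---|---|---|
| 5, 2 | 0.93 | 10.1 |
| 6, 2 | 0.76 | 11.2 |
| 7, 1 | 0.98 | 12.0 |
| 7, 2 | 0.44 | 11.7 |
| 8, 1 | 0.76 | 12.0 |
| 8, 2 | 0.13 | 11.9 |

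An all-zero table is likely while mean peaks stay around 5% to 6%. By 8% it needs a narrow spread.

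**5. What an observed 0/12 would mean.** The two-sided 95% Clopper-Pearson upper limit is 1 − 0.025^(1/12) = 26.5%. That bounds the proportion above 10% and is silent on any shift below it.

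**The case against.** The other side has several good points.

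- **The 10% cut is not arbitrary.** Protocol 7.4.1 and 7.4.2 act at roughly that level when a Grade 3 event accompanies it, and Protocol 7.4.6 describes levels up to 10% as usually without symptoms. This stands: 10% belongs in the table, but not alone.
- **A reader might infer that the 15% threshold goes unreported.** The documents do not support that. Anyone at 15% or more is also above 10%, so is counted and listed. A value that interrupts dosing should also be captured as an AE (Protocol 9.2.7) and appear in the AE dose-modification tables (SAP 7.6.4) and the delay and reduction summaries (SAP 7.4.2). What is missing is only a separate count.
- **A reader might infer that every post-baseline value above ULN is treatment-emergent**, because entry requires a value within it. That does not follow. The screening sample may be up to 14 days old, a further sample is due before the first dose, and SAP 6.1 takes the latest such value as baseline. That value could already exceed the ULN. Other agents that raise methemoglobin are allowed with caution (Protocol 7.7.2).
- **The missing by-time-point summary is not special to methemoglobin.** SAP 7.6.10.1 to 7.6.10.3 use worst-grade and shift tables throughout, and Protocol 10.3 calls its own text a summary. This stands in part. Those sections still list the named parameters without a cut-off and show shifts from baseline; the methemoglobin section does neither.
- **A reader might extend the point to ECGs**, where the SAP says only that "summary measures (n, mean, standard deviation, median, minimum, and maximum) will be provided". The pattern differs: SAP 7.6.12 lists all ECG measures by subject, so no value is hidden by a cut-off.
- **Further outputs may exist.** SAP 9 refers to a Data Presentation Plan that is not available here, and some safety text is redacted. An extra methemoglobin output cannot be excluded, but the readable SAP does not require one.

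**Conclusion.** The point holds in a limited form. A participant whose methemoglobin peaks above the ULN but no higher than 10% appears in no methemoglobin output the SAP specifies, despite the protocol's use of the ULN and its commitment in 10.3.2. Values of 15% or more are reported, but not distinguished from values just over 10%. An asymptomatic rise that stays below 10% and is not judged clinically significant would probably be missed by the AE tables too.

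The textual gap needs no assumption. Its size does: the 0/12 result is an illustration resting on an assumed 1% baseline, a ULN of 1% to 3% and chosen peaks. It does not forecast what this trial will show. The number treated may also exceed 12, because participants who leave before or at Cycle 1 Day 1 are replaced (Protocol 5.2).

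A reader might go further and infer that the sponsor's dose review would be misled. The documents do not show that: the review uses all the safety data (Protocol 7.4), and the sponsor receives every laboratory result (Protocol 9.4.1). The weakness lies in the planned reporting, and it should be corrected.

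**What to change.** Amend SAP 7.6.10.4 to provide, by phase:

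1. A by-subject listing of all methemoglobin values for all treated participants, with the ULN of the reporting laboratory and the linked reticulocyte, haptoglobin and LDH results.
2. A summary of value and change from baseline by nominal visit, as Protocol 10.3.2 states, using the SAP 6.1 baseline.
3. Counts by worst post-baseline category (≤ULN; >ULN to 10%; >10% to <15%; ≥15%), shown against baseline status so that a value already raised before the first dose is not read as a drug effect.

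The planned >10% count remains available as the sum of the last two categories. The cost is SAP wording and a few table and listing rows on data already collected. It needs no new sample, visit or participant, and it changes no dosing or clinical rule.

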### **7.6.10.5 Additional Analyses**

In addition, further analyses on specific laboratory parameters will be performed:

#### Abnormal Hepatic Function Test

The number of subjects with the following laboratory abnormalities from on-treatment evaluations will be summarized:

- ALT or AST > 3 x ULN, > 5 x ULN, > 10 x ULN and > 20 x ULN
- Total bilirubin > 1.5 x ULN and > 2 x ULN
- Concurrent (within 1 day) ALT or AST > 3 x ULN and total bilirubin > 2 x ULN
- Concurrent (within 30 days) ALT or AST > 3 x ULN and total bilirubin > 2 x ULN

A by-subject listing of these specific abnormalities will be provided.

#### Abnormal Thyroid Function Test

The number of subjects with the following laboratory abnormalities from on-treatment evaluations will be summarized:

- TSH value > ULN and
  - with baseline TSH value  $\leq$  ULN
  - with at least one FT3/FT4 test value < LLN within 2-week window after the abnormal TSH test
  - with all FT3/FT4 test values  $\geq$  LLN within 2-week window after the abnormal TSH test
  - with FT3/FT4 missing within 2-week window after the abnormal TSH test
- TSH < LLN and
  - with baseline TSH value  $\geq$  LLN
  - with at least one FT3/FT4 test value > ULN within 2-week window after the abnormal TSH test
  - with all FT3/FT4 test values  $\leq$  ULN within 2-week window after the abnormal TSH test
  - with FT3/FT4 missing within 2-week window after the abnormal TSH test

A by-subject listing of these specific abnormalities will be provided.

### **7.6.11 Vital Signs and Pulse Oximetry**

Vital signs will be summarized by timepoint.

Vital signs and pulse oximetry (i.e. % oxygen saturation) collected on the CRF will be provided in separate listings.

### **7.6.12 Electrocardiograms**

All of the available ECG parameter values from each subject will be included in the ECG data set.

Baseline values are defined as the last recorded values prior to the first dosing. For ECG parameters such as heart rate (HR), QT, QRS, QTcB, QTcF and PR, summary measures (n, mean, standard deviation, median, minimum, and maximum) will be provided.

A by-subject listing of all ECG measures and a listing of abnormal ECG interpretations will be provided.

### **7.6.13 Physical Measurements**

Physical measurements will be listed by subject.

### **7.6.14 Immunogenicity Analysis**

Further details on immunogenicity [REDACTED] definitions, population for analyses and endpoints are described in [APPENDIX 2](#).

#### **Incidence of ADA**

Number (%) of subjects will be reported for the following parameters based on Evaluable Subjects.

- Baseline ADA-positive
- ADA-positive
  - Persistent Positive (PP)
  - Not PP-Last Sample Positive
  - Other positive
  - Neutralizing Positive
- ADA-negative

A listing of all ADA assessments will be provided. A separate listing of ADA assessments of nivolumab for subjects with neutralizing positive will also be provided.

#### **Clinical implications**

Clinical implications of nivolumab immunogenicity will be primarily focused on subjects with persistent ADA-positive relative to ADA-negative. Subjects with any ADA-positive samples after initiation of treatment (relative to baseline) may be used to explore clinical implications. Effect of immunogenicity on safety will be explored by examining the type of AEs [REDACTED] such as hypersensitivity/infusion reaction. Individual subject's safety profile will be examined and described based on a listing. Clinical implications on efficacy will also be explored similarly. Association between trough concentrations of nivolumab and ADA assessments may be explored, as needed.

### **7.6.15 Pregnancy**

A by-subject listing of pregnancy tests results will be provided for treated female subjects.

## **7.7 Pharmacokinetics**

The BMS-986205 and nivolumab concentration data obtained in this study will also be combined with data from other studies in the clinical development program to develop a population PK

model. This model will be used to evaluate the effects of intrinsic and extrinsic covariates on the PK of BMS-986205 and nivolumab/IDO1 inhibitor. In addition, exposure-response analyses with selected efficacy and safety endpoints may be conducted. Results of population PK and exposure response-analyses will be reported separately.

### **7.7.1      *Pharmacokinetic Concentrations***

Analyses for this section will be provided by the CPAR group. Summary statistics and listings will be provided for the following pharmacokinetic concentrations by treatment, cycle, study day and time on the BMS-986205 and nivolumab PK Subjects.

- Plasma concentrations of BMS-986205 and select metabolites
- Serum concentrations of nivolumab

Plots of the individual and mean concentration profile vs. time by cycle/study day for BMS-986205 and select metabolites will be provided.

A by-subject listing of BMS-986205/select metabolites plasma and nivolumab serum concentrations will be provided.

### **7.7.2      *Pharmacokinetic Parameters***

Summary statistics will be provided for all individual PK parameters by treatment, cycle, study day and time where data is available. Geometric means and coefficients of variation will be presented for the selected following PK parameters for BMS-986205 or corresponding metabolites: Cmax, AUC(TAU), CLT/F, Ctrough, AI, %UR24, MR\_AUC(TAU) and MR\_Cmax. Mean and standard deviation will be presented for T-HALF(T-HALFeff\_AUC). Median, minimum, and maximum will be presented for Tmax. Drug accumulation indices (AI) is defined as the ratio of AUC(TAU) and Cmax at steady state to after the first dose. Effective T-Half, which will be calculated only if AI > 1, is defined as following:

$$\text{Effective T - Half} = \frac{\text{dosing interval} * \log(2)}{\log\left(\frac{AI}{AI - 1}\right)}$$

Plot of geometric mean with 90% CI of Ctrough vs. study day and cycle will be presented to assess if steady state is reached.

Summary statistics will be provided for the following PK parameters for nivolumab: Ctrough, Ceoi.

A by-subject listing of BMS-986205/select metabolites and nivolumab PK parameters will be provided.

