9.5.1 Pharmacokinetic Assessment following Monotherapy of BMS-986205

The PK parameters to be assessed for BMS-986205 following multiple dose administration in Cycle 0 during the dose escalation phase may include but not limited to:

Cmax	Maximum observed plasma concentration
Tmax	Time of maximum observed plasma concentration
Ctrough	Trough observed plasma concentration
AUC(TAU)	Area under the concentration-time curve in one dosing interval
CLT/F	Apparent total body clearance
Vss/F	Apparent volume of distribution at steady-state
AI	Accumulation index, calculated based on ratio of AUC(TAU) and Cmax at steady state to after the first dose
T-1/2 (eff, AUC)	Effective elimination half-life that explains the degree of AUC accumulation observed
%UR24	Percent urinary recovery over 24 hours

9.5.2 *Pharmacokinetic Assessment following Combination Therapy of BMS-986205 and Nivolumab*

Plasma samples for BMS-986205 will be collected for all participants receiving combination treatment of BMS-986205 and nivolumab. PK will be assessed for BMS-986205 when in combination of nivolumab (Cycle 1 Day 1).

Serum samples for nivolumab PK and immunogenicity assessments will be collected for all participants receiving combination treatment of BMS-986205 and nivolumab. End-of-infusion (Ceoi) and trough (Ctrough) concentrations will be tabulated using summary statistics. These data may also be pooled with other datasets for population PK analysis, which will be presented in a separate report.

Detailed sampling schedules to be followed for the assessment of PK and immunogenicity for all analytes in the study are provided in [Table 9.5.2-1](#). All time points are relative to the start of BMS-986205 dosing. Predose samples should be taken within 30 minutes before the start of BMS-986205 administration. Nivolumab end-of-infusion samples should be taken just prior to the end of infusion (preferably within 2 minutes).

Further details of sample collection, processing, and shipment will be provided in the laboratory procedures manual. On-treatment PK samples are intended to be drawn relative to actual dosing days; if a dose occurs on a different day within the cycle due to delays or minor schedule adjustments, PK samples should be adjusted accordingly.

Table 9.5.2-1: Pharmacokinetic, Anti-Drug Antibody (ADA) for BMS-986205 and Nivolumab

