10.3.3 Pharmacokinetic Analyses

Endpoint	Statistical Analysis Methods
BMS-986205 Cmax, AUCtau, CLT/F, Vss/F	Summary statistics: geometric means and coefficients of variation
BMS-986205 T-HALF(eff, AUC)	Summary statistics: means and SD
BMS-986205 Tmax	Summary statistics: medians and ranges
BMS-986205 Ctrough	Summary statistics to assess attainment of steady state: geometric means and coefficients of variation; plots vs time by dose
BMS-986205 %UR	List will be presented for %UR. Plots of individual cumulative percent of dose recovered in urine versus end of interval time. Mean plots of cumulative percent of dose recovered in urine versus end of interval time
[REDACTED]	
Nivolumab end of infusion (Ceoi), Ctrough	Summary statistics

[figure not shown]

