### **5 SAMPLE SIZE AND POWER**

The sample size for this study is not based on statistical power, but based on consideration of the precision of the estimate of geometric means of Cmax and AUC of BMS-986205. Based on preliminary PK results from Study CA017003 cohorts 25 mg to 200 mg, assuming the inter-subject CV for AUC24 is 42%, a sample size of 12 PK evaluable subjects will be sufficient for the point estimates of the mean PK parameter to fall within 80% to 125% of the true value, with 91% confidence level. Assuming the inter-subject CV for Cmax is 29%, a sample size of 12 PK evaluable subjects will be sufficient for the point estimates of the mean PK parameter to fall within 80% to 125% of the true value, with 98% confidence level. Twelve subjects will provide 90% probability of observing at least one occurrence of a specific AE that would occur with an 18% incidence in the population.

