**Table 6.2-1: Treatment Regimen Information**

| Phase       | Treatment Regimen Description                     |
|-------------|---|
| Lead-in     | BMS-986205 100 mg PO QD                           |
| Combination | BMS-986205 100 mg PO QD + Nivolumab 480 mg IV Q4W |

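### If BMS-986205 accumulates little, averaging effective half-life only over participants with AI above 1 overstates it, and the SAP does not require the number left out to be shown

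*SAP*

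**What the plan says.** SAP 7.7.2 (Pharmacokinetic Parameters) defines the index: "Drug accumulation indices (AI) is defined as the ratio of AUC(TAU) and Cmax at steady state to after the first dose". It then gives the half-life formula with its condition: "Effective T-Half, which will be calculated only if AI > 1, is defined as following". On the summary it says: "Mean and standard deviation will be presented for T-HALF". Protocol 10.3.3 plans the same statistic for this parameter, "Summary statistics: means and SD", and does not mention the condition.

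Protocol 9.5.1 describes the parameter as "Effective elimination half-life that explains the degree of AUC accumulation observed". The AUC ratio is therefore the relevant index, although SAP 7.7.2 defines AI for both AUC(TAU) and Cmax and does not say which one enters the formula.

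SAP 7.7.2 also presents the geometric mean and coefficient of variation of AI, with no AI > 1 restriction, and a by-subject listing of PK parameters. SAP 6.3 keeps a participant in the evaluable PK population on the strength of one evaluable parameter. Someone with AI at or below 1 therefore stays in the other PK summaries and is absent only from the half-life row. Neither document says how such participants enter the half-life summary or that they will be counted.

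**The concern.** AI is a ratio of two measured exposures in the same person. If true accumulation is modest, measurement and day-to-day variation can put some participants at or below 1. The half-life formula rises with AI and tends to 0 h as AI falls to 1, so the participants left out are always those at the low end. The mean of the rest can be too high but never too low for this reason.

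Two rows of one table could then rest on different people: AI on all evaluable participants, half-life on those above 1. A half-life meant to explain the observed accumulation might not match it. PK parameters are part of the primary endpoint, effective half-life is the only half-life the documents name for BMS-986205, and the study plans 12 PK-evaluable participants, so losing a few would be noticeable.

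**Working it through.** **The plan's own figures.** The documents give no figure for AI or half-life. The nearest stated figures are the precision statements in SAP section 5 for 12 PK-evaluable participants. With SE = sqrt(ln(1 + CV²)/12) and a t distribution on 11 df, the probability of falling within 80% to 125% is 91.9% for AUC (CV 42%) and 98.0% for Cmax (CV 29%). With SD set equal to the CV, the results are 90.7% and 97.8%. The plan states 91% and 98%, so these reproduce. They do not help here: "assuming the inter-subject CV for AUC24 is 42"% describes spread between participants, not noise in one participant's ratio of two AUCs.

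**Inputs.**
- Dosing interval 24 h, from "BMS-986205 100 mg PO QD" (SAP Table 6.2-1).
- n = 12 (SAP section 5).
- Formula T = 24 × ln 2 / ln(AI/(AI − 1)) (SAP 7.7.2). It is the inverse of AI = 1/(1 − 2^(−24/T)), the standard relation.
- Assumed, because the documents give neither: the centre of AI, from 1.1 to 3, and log-normal variation of observed AI with log-SD s of 0.2 or 0.3.

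**Step 1: half-life at a given AI.** 24 × ln 2 = 16.64.
- AI 1.1: 16.64 / ln 11 = 6.9 h
- AI 1.25: 16.64 / ln 5 = 10.3 h
- AI 1.5: 16.64 / ln 3 = 15.1 h
- AI 2: 16.64 / ln 2 = 24.0 h
- AI 3: 16.64 / ln 1.5 = 41.0 h

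**Step 2: share excluded.** p = P(observed AI ≤ 1) = Φ(−ln(AI)/s). For AI 1.1 and s = 0.3, Φ(−0.0953/0.3) = Φ(−0.318) = 0.375, or 12 × 0.375 = 4.5 of 12.

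**Step 3: selection effect alone.** Compare the mean over AI > 1 with the mean over everyone, holding AI ≤ 1 at the formula's limit of 0 h. The second mean equals (1 − p) times the first, so the inflation is p/(1 − p). For AI 1.1 and s = 0.3, 0.375/0.625 = +60%.

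| AI | s | p | expected excluded of 12 | mean, AI > 1 only (h) | mean, all, AI ≤ 1 as 0 (h) | selection effect |
|---|---|---|---|---|---|---|
| 1.1 | 0.2 | 0.317 | 3.8 | 9.6 | 6.6 | +46% |
| 1.1 | 0.3 | 0.375 | 4.5 | 11.8 | 7.4 | +60% |
| 1.25 | 0.2 | 0.132 | 1.6 | 11.6 | 10.1 | +15% |
| 1.25 | 0.3 | 0.228 | 2.7 | 13.7 | 10.6 | +30% |
| 1.5 | 0.2 | 0.021 | 0.3 | 15.7 | 15.4 | +2% |
| 1.5 | 0.3 | 0.088 | 1.1 | 17.3 | 15.7 | +10% |
| 2 | 0.2 | 0.0003 | 0.003 | 24.6 | 24.6 | 0% |
| 2 | 0.3 | 0.010 | 0.1 | 25.6 | 25.3 | +1% |
| 3 | 0.3 | 0.0001 | 0.002 | 43.3 | 43.3 | 0% |

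**Step 4: separate selection from averaging.** At AI 2 the surviving mean exceeds the 24.0 h from step 1 by about 7% (s = 0.3) or 3% (s = 0.2), yet selection supplies only 1% and 0%. The remainder comes from taking an arithmetic mean of a noisy, non-linear transform. At AI 3, where almost nobody is excluded, the same comparison still shows 2% to 6%.

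**Step 5: check the remedy.** When AI ≤ 1 is ranked lowest, the median over all participants equals the half-life at the geometric mean AI under this model (6.9 h at AI 1.1, 15.1 h at 1.5, 24.0 h at 2). Back-transformed limits can fail, however. At AI 1.1, s = 0.3 and n = 12, the lower 90% limit of AI is 1.1 × exp(−1.796 × 0.3/√12) = 0.94, for which the formula has no value. A rule is needed for that case.

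**The case against.** The best defence is that the condition is forced. At AI = 1 the formula divides by zero, and below 1 it takes the logarithm of a negative number. A reader might infer that the AI > 1 rule is itself a mistake; it is not. That stands, and only the way the truncated set is summarised is open to criticism.

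A reader might also infer that the reported half-life will be biased upward whatever the data show. The documents do not support that. They give no expected AI, no expected half-life and no within-subject variance, and at AI of about 2 or more almost nobody would be excluded. Nor should the whole excess over the half-life at the true AI be blamed on exclusion, as step 4 shows.

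The plan also offers some transparency. The geometric mean AI and the by-subject listing would let a careful reader count the exclusions and redo the calculation. SAP 8.2 refers PK exclusions and reporting to a harmonization document, and SAP section 9 leaves the list of analyses to a Data Presentation Plan. Neither is available here, so a counting rule may exist there. This lowers the importance, but a traceable exclusion does not correct the printed mean.

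Finally, the sample size rests on Cmax and AUC, and no hypothesis or success criterion uses half-life. The parameter lists are open-ended, and population PK is reported separately. All of that stands and keeps the point minor.

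**Conclusion.** The point holds conditionally and is minor. SAP 7.7.2 averages a set from which only the lowest values can be missing, with no stated count and no companion estimate using everyone. If AI is near 1, the upward selection effect is material: about +46% to +60% at AI 1.1 and +15% to +30% at 1.25. It falls to +2% to +10% at 1.5 and is practically nil at 2 or more.

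These sizes assume log-normal variation in observed AI with a log-SD of 0.2 to 0.3, and a limiting half-life of 0 h for AI at or below 1. The direction needs only that the formula increases with AI. Which row of the table applies cannot be settled from the documents. The sample size and the other PK summaries are unaffected.

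**What to change.** In SAP 7.7.2:

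1. Keep the protocol's mean and SD, and print beside them the number of evaluable participants with AI at or below 1.
2. Add the half-life obtained by putting the geometric mean AUC-based AI of all evaluable participants into the same formula, with confidence limits back-transformed. Where the lower AI limit is 1 or less, show that half-life limit as not estimable (approaches 0). Do the same for the estimate if the geometric mean AI itself is 1 or less.
3. Add the median and range of individual values, with AI at or below 1 ranked lowest instead of treated as missing.
4. State that the AUC-based AI, not the Cmax-based one, enters the formula.

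The cost is a few sentences in the SAP and a few extra summary rows. No new data are needed.
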